2.2 Analysis sets

The following analysis sets will be used in the analyses:

- Enrolled set: All patients who are enrolled, i.e. who signed informed consent, are included in the Enrolled set.
- Safety set: The Safety set includes all patients who received at least one dose of study drug.
- Full Analysis set (FAS): The FAS includes all patients who received at least one dose of study drug and had at least one post-baseline efficacy assessment.

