8.3 Database management and quality control

Novartis staff (or designated contract research organization (CRO) staff) review the data entered into the CRFs by Investigator/qualified study center staff for completeness and accuracy and instruct the study center personnel to make any required corrections or additions.

Queries are sent to the study center using an electronic data query. The Investigator/qualified study center staff are required to respond to the query and confirm or correct the data. If the electronic query system is not used, a paper Data Query Form will be faxed to the study center. Study center personnel will complete and sign the faxed copy and fax it back to Novartis staff who will make the correction to the database. The signed copy of the Data Query Form is kept at the Investigator study center.

Concomitant medications entered into the database will be coded using the WHO Drug Reference List, which employs the Anatomical Therapeutic Chemical classification system. Concomitant procedures, non-drug therapies and AEs will be coded using the Medical dictionary for regulatory activities (MedDRA) terminology.

Laboratory samples will be processed centrally and the results will be sent electronically to Novartis (or a designated CRO).

Medical history and AEs will be coded using MedDRA terminology.

Efficacy assessments (IGA mod 2011, PASI and BSA) will be performed using an electronic device or paper forms. In case electronic devices are used but there is a data collection failure, a paper-based process is acceptable and details of the whole process are described in a separate user manual.

PROs assessments (DLQI, EQ-5D[®], NRS (itching, scaling and pain VAS), HAQ[®]-DI, TSQM and PBI) will be performed using electronic devices or paper forms. In case electronic devices are used but there is a data collection failure a paper-based process is acceptable and details of the whole process are described in a separate user manual.

All efficacy assessments and PRO assessments will be maintained in a central database and in case the database is managed by a vendor results will be sent electronically to Novartis (or a designated CRO).

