9.1 Analysis sets

The following analysis sets will be used in the analyses:

Enrolled set: All patients who are enrolled are included in the Enrolled set.

Safety set: The Safety set includes all patients who received at least one dose of study drug.

Full Analysis set: The Full Analysis set includes all patients who received at least one dose of study drug.

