9.4 Analysis of the primary variable

9.4.1 Variable

The primary analysis variable is the proportion of patients achieving a DLQI 0/1 response at Week 16 in 3 pre-defined subpopulations and in the overall study population.

The analysis of the primary variable will be based on the Full Analysis set.

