10	20	141	Day 128 – Day 155	Day 128 – Day 155			
11	24	169	Day 156 – Day 211	Day 156 – Day 211	Day 142 – Day 211		
12	36	253	Day 212 – Day 295	Day 212 – Day 295	Day 212 – Day 295		
13	48	337	Day 296 – Day 351	Day 296 – Day 351	Day 296 – Day 351	Day 226 – Day 351	
14	52	365	Day 352 – Day 379	Day 352 – Day 379	Day 352 – Day 379	Day 352 – Day 379	Day 240 – Day 379

a: Body Surface Area (BSA), PASI, IGA mod 2011

b: laboratory sampling (Hematology, Chemistry and Urinalysis) and vital signs

c: NRS, DLQI, EQ-5D, HAQ-DI, TSQM, PBI

e: Fasting laboratory

f: (weight, waist and hip circumference)

In the case of major deviations from the visit schedule, or due to unscheduled visits, several assessments of a subject may fall in a particular visit window (either scheduled or unscheduled). In this case, the following rules are applied to select one value “representing”

the subject in summary statistics in a visit window. For baseline assessment definition see Section for Baseline above. For post-baseline visit windows the following applies:

- for *quantitative variables and qualitative efficacy variables*, the closest to the actual visit is chosen (if two assessments have the same distance, then the earlier one will be chosen);
- for *qualitative safety variables*, the worst record is selected. It is noted that in the analyses performed, worst case is always well defined (e.g., for urine dipstick values “+” and “++”, the worst case is defined as “++”),
- in case *qualitative variables are based on quantitative variables*, e.g. PASI 75 response, the visit will be assigned to the quantitative variable, and this visit will be used for the derived qualitative variable.

For the analysis of assessments done at Screening, the Screening visit will be analyzed as reported on the eCRF.

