2.5 Analysis of the primary objective

2.5.1 Primary endpoint

The primary analysis variable is the proportion of patients achieving a DLQI 0/1 response at Week 16 in 3 pre-defined subpopulations and in the overall study population.

The analysis of the primary variable will be based on the FAS.

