2.7 Analysis of secondary efficacy objective(s)

2.7.1 Secondary endpoints

- To assess the proportion of patients achieving a DLQI 0/1 response at Week 52 in the 3 subpopulations and in the overall study population.
- To assess the effects of treatment with secukinumab 300 mg with respect to changes in EQ-5D, HAQ-DI, NRS, TSQM and PBI response over time up to Week 16 and Week 52 compared to baseline in the 3 subpopulations and in the overall study population.
- To assess the proportion of patients achieving PASI 50, PASI 75, PASI 90, PASI 100 and IGA mod 2011 0/1 responses at Week 16 and Week 52 in the 3 subpopulations and in the overall study population.
- To assess the proportion of patients with DLQI scores 2-5, 6-10, 11-20, 21-30 at Week 16 and Week 52 compared to baseline in the 3 subpopulations and in the overall study population.
- To assess the overall safety and tolerability of treatment with secukinumab 300 mg in the 3 subpopulations and in the overall study population.

The analyses of the secondary efficacy endpoints will be performed on the FAS, overall and by subpopulation.

The analysis of the secondary endpoint regarding safety will be described in the safety section 2.8.

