2.14 Interim analysis

An interim analysis describing the self-reported baseline characteristics and HR-QoL of patients prior to treatment will be performed for this study after LPFT.

The interim analysis will be based on the Safety set.

Patient screening phase disposition, demographics, baseline disease characteristics, baseline IGA mod 2011, PASI and PROs will be presented as described in [Section 2.3](#).

Other medical history and prior medications and non-drug therapies will not be part of the interim analysis.

3 Sample size calculation

The study aims to estimate primarily the effect of 16 weeks treatment with secukinumab 300 mg on the QoL of the overall study population as well as within the 3 pre-defined subpopulations. It is expected that 40% of the overall study population will fulfil the criteria

for the definition of subpopulation A; 40% will fulfil the criteria for subpopulation B; and 20% will fulfil the criteria for subpopulation C.

The DLQI 0/1 response rate in the overall population treated with secukinumab 300 mg s.c. is expected to be around 70% at Week 16; however, it may vary within those pre-defined subpopulations. A total of 323 patients are required to estimate the response rate of DLQI 0/1 with a precision (= 95% CI) of 5% if the true response rate is about 70% in the smallest subpopulation. To ensure that this precision is achieved in the 3 subpopulations (defined in Section 3.1), which consist of 20% to 40% of the overall study population, 1 615 patients in total should be recruited into this trial.

4 Change to protocol specified analyses

According to the protocol all data from physical examinations should be summarized and listed. As these data are only collected in the source data (see Section 6.5.1 of the protocol) this will not be analyzed.

5 Appendix

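### The SAP narrows the primary analysis set without declaring it, and no sensitivity analysis of the Week 16 DLQI 0/1 rate is allowed

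*SAP*

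**What the plan says.** The two definitions of the primary analysis set differ.

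- Protocol 9.1: "The Full Analysis set includes all patients who received at least one dose of study drug".
- SAP 2.2: "The FAS includes all patients who received at least one dose of study drug and had at least one post-baseline efficacy assessment".

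Both documents use the set for the primary endpoint. Protocol 9.4.1 says "The analysis of the primary variable will be based on the Full Analysis set", and SAP 2.5.1 says "The analysis of the primary variable will be based on the FAS". SAP 2.7.1 uses it for the secondary efficacy endpoints too: "The analyses of the secondary efficacy endpoints will be performed on the FAS, overall and by subpopulation".

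SAP Section 4 is the place for changes to protocol-specified analyses. Its single entry begins "According to the protocol all data from physical examinations should be summarized and listed" and explains why that will not be done. It has no entry on analysis sets.

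For missing data, Protocol 9.4.3 and SAP 2.5.3 apply LOCF to the DLQI score whatever the reason for missingness, with non-response as the default. SAP 2.5.3 adds that baseline is not carried forward; the protocol does not say this. Protocol 9.4.4 and SAP 2.5.4 both exclude sensitivity analysis of the primary variable. For Week 52, SAP 2.7.2 and 2.7.3 describe LOCF only, without expressly excluding anything else.

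**The concern.** The main point is the undeclared change of set. The study is descriptive, so the estimated proportion is its result and the denominator is part of that result. SAP Section 2 presents its methods as those of protocol section 9 in more detail, so someone reading Section 4 would take the set to be unchanged.

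The added condition is also not tied to the endpoint. Protocol 8.3 describes the efficacy measures thus: "Efficacy assessments (IGA mod 2011, PASI and BSA) will be performed using an electronic device or paper forms". It lists DLQI separately, as a patient-reported outcome. SAP 2.7 analyses DLQI among the efficacy endpoints, so the term could be wider, but on either reading one skin score is enough to qualify. SAP Table 2-1 schedules the skin scores ("a: Body Surface Area (BSA), PASI, IGA mod 2011") at all visits, from Week 1, while DLQI first appears after baseline at Visit 6 (Week 4). Two dosed patients with no post-baseline DLQI can therefore be treated differently. One with a Week 1 PASI stays in the denominator as a non-responder, which follows from SAP 2.1 and 2.5.3 although neither spells it out. One with no post-baseline assessment disappears.

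The second point is that nothing planned in the available text shows how far the primary rate depends on LOCF. The percentage of imputed scores is to be reported, but it only bounds the effect: with 5% imputed, LOCF exceeds non-responder imputation (NRI) by anything from 0 to 5 points.

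**Working it through.** **The plan's own figure.** Protocol 9.7 and SAP Section 3 give a 70% rate, 5% precision at 95%, and 20% of patients in the smallest subpopulation. n = 1.96² × 0.70 × 0.30 / 0.05² = 322.68, rounded up to 323; 323 / 0.20 = 1,615. Both match, so the 5% is a half-width. There is no allowance for exclusions or dropout.

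**Planned half-widths (h).** The SAP 5.6.1 interval (score method with continuity correction) at p = 0.70:

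| Group | n | 95% CI | h (points) |
|---|---|---|---|
| C | 323 | 64.63-74.88% | 5.13 |
| A or B | 646 | 66.28-73.48% | 3.60 |
| Overall | 1,615 | 67.69-72.22% | 2.26 |

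**Effect of the narrower set.** Let f be the share of dosed patients excluded and b the share of those who would have counted as responders. If the rate on all dosed patients is 0.70, the rate on the SAP set is (0.70 − f·b)/(1 − f). The documents do not give f; 0.5-2% (8-32 of 1,615) is assumed.

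| f | b = 0 (SAP rule) | b = 0.10 (baseline carried, assumed) |
|---|---|---|
| 0.5% | 70.35% | 70.30% |
| 1% | 70.71% | 70.61% |
| 2% | 71.43% | 71.22% |

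The sign reverses only if b exceeds 0.70, that is, if more than about 70% of the excluded patients had DLQI 0/1 at baseline and baseline could be carried. With b = 0, the shift equals the half-width at f = h/(0.70 + h): 3.1% overall (51 patients), 4.9% in A or B (32) and 6.8% in C (22).

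**LOCF minus NRI.** The gap is m·s, where m is the share missing and s the share of those at DLQI 0/1 when last seen. Both are assumed.

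- Week 16, m = 3-8%, s = 30-70%: from 0.03 × 0.3 = 0.9 points to 0.08 × 0.7 = 5.6 points.
- Week 52, m = 10-20%, same s: from 0.10 × 0.3 = 3 points to 0.20 × 0.7 = 14 points.

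The share missing at which the gap equals the half-width is m = h/s:

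| Group | s = 0.3 | s = 0.5 | s = 0.7 |
|---|---|---|---|
| Overall | 7.5% | 4.5% | 3.2% |
| A or B | 12.0% | 7.2% | 5.1% |
| C | 17.1% | 10.3% | 7.3% |

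**Both parts together.** Take the SAP rate as 70% and subtract NRI on all dosed patients: 0.70 − (1 − f)(0.70 − m·s).

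- Week 16, low: 0.70 − 0.995 × (0.70 − 0.009) = 1.25 points. High: 0.70 − 0.98 × (0.70 − 0.056) = 6.89 points.
- Week 52, also assuming a 70% rate, low: 0.70 − 0.995 × (0.70 − 0.03) = 3.33 points. High: 0.70 − 0.98 × (0.70 − 0.14) = 15.12 points.

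**Against the true rate.** LOCF error is m·(s − t), where t is the true response share among the missing. Its sign is unknown. With s and t each between 0.30 and 0.70, it is at most 0.08 × 0.40 = 3.2 points either way at Week 16. That is below the half-width in each subpopulation and above the overall 2.3.

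**The case against.** The strongest case is that this is a small documentation gap.

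- The all-dosed rate can be recovered. The SAP Safety set is defined as the protocol's Full Analysis set is. Set sizes are tabulated and responder counts reported, so a reader can divide responders by the Safety-set number. This stands under the SAP rule, but it needs a reader who has noticed the change, and the available text plans no such rate.
- Exclusions should be few. Skin scores start at Week 1, and Protocol 5.6.2 asks for end-of-treatment assessments in patients who stop the drug. Exclusion needs a dosed patient with no later assessment, mainly after early consent withdrawal or loss. This stands and supports a low f. It limits the size of the shift but does not justify leaving it undeclared.
- The two documents agree on having no sensitivity analysis, so the SAP introduced nothing there. With one regimen and no test, no formal decision depends on LOCF. This stands: the second point asks for a missing check and alleges no contradiction.
- The larger figures come from assumed dropout, and Week 52 is secondary. This is correct, and they do not carry the main point.
- SAP 2.13, to which SAP 2.11 refers for exploratory analyses, is not in the available text. No judgement is made on it.

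**Conclusion.** The concern holds. The SAP changes the primary analysis set from the one the protocol defines and does not declare it. Under the SAP's own missing-data rule the change can only raise the DLQI 0/1 rate. The rise is probably small: 0.4-1.4 points if 0.5-2% of dosed patients are excluded. It would reach the planned half-width only at about 3% excluded overall, 5% in A or B, or 7% in C.

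The missing-data choice may matter more, and no planned output in the available text estimates its effect on the primary rate. All dropout, exclusion and last-seen response shares used here are assumptions. This should be fixed, because the denominator of a descriptive primary result must match the protocol or be declared.

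**What to change.** 1. In SAP 2.2, restore the protocol definition (all dosed patients), and state that a patient with no post-baseline DLQI counts as a non-responder. If the narrower set is kept for any table, define what counts as an efficacy assessment, and declare and justify the set in SAP Section 4.
2. Keep LOCF as the primary rule. Replace the exclusion of sensitivity analysis with a prespecified NRI analysis on all dosed patients, supported by observed cases, for DLQI 0/1 at Weeks 16 and 52, overall and by subpopulation. Declare it in SAP Section 4, since Protocol 9.4.4 plans none.
3. Minor wording: LOCF step 1 in SAP 2.5.3 refers to unscheduled visits, while SAP 2.1.1 re-aligns all visits. Align the two so that early end-of-treatment assessments are windowed by their actual date.

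The cost is SAP wording, the Section 4 entry and a few more tables. Trial conduct does not change. The reported rates may be slightly lower.

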2.2.1 Subgroup of interest

All analyses will be performed by the following subpopulations:

- **Subpopulation A:** Patients who are **naïve to any systemic treatment**, e.g. patients failing or intolerant to previous topical treatment, including narrow band UVB, but never exposed to any systemic treatment, with or without contraindications to the use of conventional systemic treatment and in a need of a first systemic treatment.
- **Subpopulation B:** Patients who have been **previously exposed to at least one conventional systemic therapy**; either because of failure or intolerance to their previous conventional systemic treatment, they are in a need of a first biologic systemic treatment;
- **Subpopulation C:** Patients who have been **previously exposed to at least one biologic systemic therapy**; either because of failure or intolerance to their previous biologic systemic treatment, they are in a need of a different biologic systemic treatment.

2.3 Patient disposition, demographics and other baseline characteristics

Demographics and other baseline characteristics will be collected at Screening (Visit 1) or at Baseline (Visit 2) prior to first study drug administration for the efficacy and Patient-reported

Outcome (PRO) measurements. Summary statistics will be provided for demographic and baseline characteristics overall and by subpopulations for the Safety set.

Demographics include age, sex, race, ethnicity, height, weight, body mass index (BMI), waist and hip circumference at Screening. Age will be presented as continuous variable in years and also as categorical variable with the categories <65, >=65 and >=75 years.

Demographic data of screen failures and violated inclusion and exclusion criteria of all patients will be listed only.

Baseline disease characteristics include duration of psoriasis (in years), presence of PsA, duration of PsA, IGA mod 2011 response categories, PASI score and BSA score at Screening. PASI score will be presented as continuous variable and also as categorical variable with the categories <20, >=20.

Other baseline characteristics include smoking history and presence of tuberculosis, vital signs at Screening (i.e. systolic and diastolic blood pressure, pulse rate).

In addition baseline IGA mod 2011 response categories, PASI score, BSA score and PROs NRS (pain, itching and scaling) scores, DLQI score, DLQI subsection scores, EQ-5D (question and answer categories, VAS and Crosswalk Index Value) and HAQ-DI will be summarized. The DLQI score will be summarized as continuous variable and as categorical variable categorized into 0-1 no effect on patient's life, 2-5 small effect on patient's life, 6-10 moderate effect on patient's life, 11-20 very large effect on patient's life, 21-30 extremely large effect on patient's life. PASI score will be presented as continuous variable and also as categorical variable with the categories <20, >=20.

Baseline vital signs and laboratory values will be summarized within the safety section.

Cardiovascular history will be summarized by predefined history term overall and by subpopulation. Other medical history and current medical conditions will be summarized by MedDRA primary system organ class (SOC) and preferred term overall and by subpopulations.

2.3.1 Patient disposition

If not stated otherwise the Safety set will be used for the summary and listing of patient disposition.

The number of patients in the Safety set will be summarized by country, center and subpopulation.

The number of patients with protocol deviations will be tabulated by deviation category overall and by subpopulation. Protocol deviations will be listed with date and study day of occurrence and the population codes which show the exclusion from analysis sets.

The number of patients included in each analysis set will be tabulated.

For each study phase (i.e., screening, treatment phase 1 and treatment phase 2), the overall number of patients who entered, completed, and discontinued that phase will be summarized including the reasons for discontinuation. The summary of the screening phase will be done

for the Enrolled set, the summaries of the treatment phase 1 and 2 will be done on the Safety set overall and by subpopulation.

2.4 Treatments (study treatment, rescue medication, concomitant therapies, compliance)

2.4.1 Study treatment / compliance

The analysis of study treatment data will be based on the Safety set.

Duration (days) of exposure to study drug will be summarized. Duration of exposure is defined as:

- End of treatment phase 1 date - date of first dose of study drug + 1 for subjects discontinuing during treatment phase 1
- End of treatment phase 2 date - date of first dose of study drug + 1 for subjects completing the study or discontinuing during treatment phase 2

In addition, the number of subjects with exposure of at least certain time thresholds (“any exposure”, “≥ 1 week”, “≥ 2 weeks”, “≥ 3 weeks”, “≥ 4 weeks”, “≥ 8 weeks”, “≥ 12 weeks”, “≥ 16 weeks”, “≥ 20 weeks”, “≥ 24 weeks”, “≥ 28 weeks”, “≥ 32 weeks”, “≥ 36 weeks”, “≥ 40 weeks”, “≥ 44 weeks”, “≥ 48 weeks”, “≥ 52 weeks”) will be displayed.

The number of secukinumab injections will be presented cumulatively.

Compliance (%) will be calculated in percent as the total number of injections administered divided by the number of injections scheduled according to the protocol multiplied by 100.

2.4.2 Prior, concomitant and post therapies

Prior medications and non-drug therapies will be summarized overall and by subpopulation separately for Psoriasis therapies and non-indication medications / non-drug therapies. The same analysis as described for prior medications and non-drug therapies will be repeated for concomitant medications and non-drug therapies.

Prior therapies are defined as treatments taken and stopped prior to first dose of study drug. Concomitant therapies are defined as therapies given at least once between the day of first dose of study drug and the last day of study, including those which were started prior to first dose of study drug and continued into the treatment period or beyond.

Psoriasis therapies and non-indication medications / non-drug therapies will be presented overall, by ATC codes (level 4) and preferred term. Medications will be presented in alphabetical order of the ATC code and preferred term. Tables will also show the overall number and percentage of patients receiving at least one treatment of a particular ATC code.

In addition psoriasis therapies will be summarized by type of psoriasis therapy (biologic systemic, non-biologic systemic, topical, phototherapy, and photochemotherapy) and preferred term.

2.5 Analysis of the primary objective

2.5.1 Primary endpoint

The primary analysis variable is the proportion of patients achieving a DLQI 0/1 response at Week 16 in 3 pre-defined subpopulations and in the overall study population.

The analysis of the primary variable will be based on the FAS.

